Cluster randomisation: this works well when there are no differential pressures on recruitment between groups. For this trial a cluster randomised trial (i.e. randomising by practice) would very probably result in differential recruitment bias between groups. This study may well change such perceptions of clinicians, but we have to go from where we are: RADTs are used widely in Europe and the USA, but not currently in much use in the UK⁹, and the RADT group is likely in the current climate to be less attractive since it is more time consuming, involves some minor discomfort for patients (and in some, gagging and vomiting). Practices in the UK randomised to use RADTs alone would therefore very probably recruit less well, and with different patients in RADT and control groups. The issue of differential recruitment in cluster trials is not theoretical – it occurred recently in the MRC UKBEAM trial both in terms of differential numbers and differential characteristics of patients - where there were considerably fewer incentives for differential recruitment than the current proposed trial - and the cluster design element of the trial had to be abandoned. The other disadvantage of cluster randomisation is the additional design effect requiring inflation of the sample size.

Individual randomisation: The potential disadvantage of individual randomisation (ie. by patient within practices) relates to concerns about group differentiation: however each group will be administered using a standardised manualised approach. Our group now has extensive experience in the successful completion of 13 such trials including several recent behavioural trials, antibiotic prescribing strategy trials very similar to the current trial proposed³²⁻³⁴ and a lifestyle intervention trial.³⁵ The manualised approach maintains clear group differentiation despite individuals being randomised to different groups by the same health professional³²⁻³⁵ and the data suggest that using such an approach the health professional and practice cluster effects are minimal.^{32:36;37}

Thus our aim will be to use individual randomisation and only if this proved unfeasible in the feasibility phase then use practice based randomisation.

Planned Inclusion criteria. Previously well subjects aged 3 years an over with acute illness (2 weeks or less), presenting with sore throat as the main symptom, with an abnormal examination of the pharynx (similar criteria to previous studies of sore throat in this group¹⁹). Most patients present within 5 days, but a smaller minority present with a longer duration of illness prior to seeing the doctor.²⁷ Since we wish this sample to be representative of those patients presenting to GPs²⁷, and prior duration predicts subsequent illness duration³⁸ (i.e. an important group to help) we do not wish to exclude those with longer prior duration of illness.

Exclusion criteria. Quinsy, previous rheumatic fever, glomerulonephritis. Serious chronic disorders where antibiotics are needed (e.g. cystic fibrosis, valvular heart disease), or mental health problems (e.g. learning difficulties - unable to complete outcome measures).

Informed consent. Parents will have to sign a consent form on behalf of children. Some of the older children e.g. the 4 and 5 year olds who have some language will be able to understand the patient information leaflet, and will be encouraged to sign or mark the consent form. GCP (Good Clinical Practice) training will be provided to all participating practices, with particular emphasis on the complexities of randomising children in clinical trials

Proposed time period for retention of relevant trial documentation

Trial documentation will be kept for 15 years.

Proposed outcomes/data collection

Clinical Data: Baseline clinical data will be collected ^{25 6 26} as in phase 1. The GPs will also be asked to rate the sore throat as Viral/bacterial.

Diary scores.^{19:27} Each symptom is scored 0=no problem to 6=as bad as it could be: sore throat, difficulty swallowing, feeling unwell, fevers, sleep disturbance) which patients fill out on all days until their symptoms have resolved. A phone call from the research assistant (RA) in the first few days resolves any problems the patient may have filling out the diary. We have chose the two item score (sore throat, difficulty swallowing) as the main outcome as it is more reliable than either item alone and is internally reliable (Cronbach's alpha=0.92); these simple diaries have been used in several of our studies^{27;30;39} and are also more sensitive to change than criterion measures.⁴⁰ Temperature will be taken by patients and documented on a daily basis in the diary using tempadot thermometers as in our previous studies.^{19 39}

Duration of illness. The diaries will also allow us to document duration of illness (until very little/no problem), the duration of moderately bad illness (until rated less than a moderately bad problem)³⁰, antibiotic use, and use of over the counter medicines (also see notes review)

Antibiotic use. It is vital to document antibiotic use since rapid tests may achieve the same symptomatic benefit as the other strategies, but with the advantage of reduced antibiotic use. Our proposed method is self report, supplemented by using a box at the front reception for delayed prescriptions, and also documenting prescribing information from notes. One alternative is to trace prescriptions using stamps; this would require GPs to use stamped prescriptions and possibly make them less likely to recruit given the ease of mislaying pads/stamps (most GPs now print prescriptions); also cashing a prescription does not mean it is used³. It is also not feasible nor sensible to use more invasive methods of documenting antibiotic use (e.g. 'smart' containers, urinary antibiotic estimation etc) since these are liable to artificially alter antibiotic compliance, and thus potentially modify symptomatic outcomes. Thus our main outcome for antibiotic use is self report (i.e. to give patients 'permission' to say whether they used antibiotics or not) backed by the evidence from unused delayed prescriptions and notes review- as we have documented in our previous studies³⁻⁵. We have previously showed that self report from the diaries agreed well with whether delayed prescriptions were collected³, that self report correlated with weighed bottles for paracetamol use⁴ - supported by another study in our group which has compared self report and weighing ([name] personal communication).

Side effects. It is also important to document side effects of antibiotics since rapid tests may achieve the same symptomatic benefit as the other strategies but with the advantage of reduced side effects by minimising antibiotic use. Diarrhoea and skin rash will be documented in the diary, and also - where these are serious enough to contact the doctor – from the notes review (see below).

The medicalisation of illness. Patients' belief in the importance of seeing the doctor will be documented using 5 point Likert scales completed by patients²⁷ which we have shown to be reliable.²⁷ We will also document patients reconsultation behaviour by blinded notes review¹⁹ (see below)

Time. We will document time taken in the consultation (on the same sheets as the clinical sheets). Patients will document time off work and or time to resume normal activities in the diaries.

Socio-Demographic data. Age, gender, household income, social deprivation indices based on post code will be recorded.

Notes review. During the available follow-up time (which will vary from 1 month to 2 years) all patient's notes will be reviewed to document returns, time to return, reasons for returns, complications, side effects, economic data (see below) and any subsequent referrals.¹⁹

Sample size Phase II. 'Medicalising' effect of using RADT. (alpha=0.05, beta=0.2). This is the limiting sample size calculation although not the primary outcome. A good proxy for 'medicalising' behaviour is the change in beliefs about the need to see doctors in future episodes – assuming there are 15% differences between groups (22% were observed in our previous trial) ²⁷ then only 152 patients per group are needed (see table below). However a harder behavioural outcome is preferable: to assess the medicalising effect on reattendance behaviour; if we assume that using RADTs may change subsequent attendance by 11% (RADT 38%, clinical score 27%, delayed prescribing 27%) - as observed in the medicalising effect of prescribing strategies in a previous trial over a similar follow-up period²⁷ - then 254 patients per group are needed or 849 in total allowing for 10% loss to follow-up of notes.³⁹ An alpha of 0.01 and beta 0.1 would require an unfeasibly large sample (460 per group or >1500 patients in total) or another 2 centres for the trial.

Primary outcome: symptom severity (alpha= 0.01:beta=0.1). **Diary score.** The time when an RADT is most likely to help patients is when the inflammation due to bacterial infection is at its greatest in the first few days after seeing the doctor. We assume the minimum effect size for the symptoms severity score is a 0.33 standardised effect size (i.e. 0.33 SD) on days 2-5 is when patients rate their sore throat at its worst. To detect a 0.33 standardised effect size difference between the RADT group and control groups (assuming both control groups are 0.33 SD higher than the RADT group) requires a minimum of 134 per group (for alpha=0.05,beta=0.2) but preferably for (for alpha=0.01 and beta=0.1), 242 per group, or 909 patients in total allowing for 20% loss to follow-up of diary information.^{27;30} A standardised effect size of 0.33 is classified as a small effect size, (0.33 SD is equivalent to half patients rating sore throat a mild rather than moderately bad problem, or duration of sore throat one days difference), and in this context this order of effect size was judged to be the smallest worthy of treatment by general practitioners.³⁰ A much smaller effect size (e.g. 0.25standardised effect size) would result in an unfeasibly large sample (see table below). We will explore in the phase 1 (including the qualitative work) whether such an effect size (i.e. 0.33 SD) is regarded by patients as being the minimal worth treating, and what effect size would be regarded as equivalent. An alpha of 0.01 is preferable since it allows for type I error - with 2 comparisons between RADT and the other two groups, and also for multiple outcomes (severity/duration), and a beta of 0.1 will help ensure that we do not miss an effect in our primary outcome.

outcome are in bold).	Difference between RADT group and other two groups	Alpha 0.01 Beta=0.1	Alpha 0.01 Beta=0.2	Alpha 0.05 beta=0.2
Standardised effect size (continuous outcomes e.g. symptom severity,duration, time to first return for sore throat)	0.5 (i.e. RADT 0.5 lower than other 2 groups)	107	85	59
	0.33	242	193	134
	0.25	420	335	233
'Medicalisation' and antibiotic use:				
Proportions: behaviour (return to surgery); antibiotic use	11% (38%, 27%, 27%)	460	366	254
	15% (42%, 27%, 27%)	253	202	140
	20% (47%, 27%, 27%)	146	117	81
Proportions: beliefs (in the need to see the doctor; belief in antibiotics)	15% (57%,57%,72%)	274	219	152
	20% (57%, 57%, 77%)	152	121	84

Sample size in each group¹-range of options for Phase II trial (our proposed sample sizes for each outcome are in **bold**).

1. We used the NQUERY multiple group sample size programme for three groups and assumed both clinical score and control groups had similar figures; if the control group fares worse than the clinical score group (i.e. the spread of observations is wider) fewer numbers will be needed in each group. The numbers in each cell are the numbers with complete data required in each group.

Statistics analysis, type and frequency

We will perform analysis of covariance for the main continuous outcomes (diary scores, symptom duration). Log rank tests and Cox regression will be used to assess the time to return to the surgery with a new episode of sore throat as we used in our previous trial¹⁹ (which will involve 'censored' data due to variable follow-up time available). Logistic regression will be used for dichotomised outcomes (e.g. belief in the need to see the doctor, belief in antibiotics) and Poisson regression for incidence rates (e.g. rates of return to the surgery with sore throat - which more closely follow a Poisson distribution rather than a normal distribution). The models will control for confounders if appropriate (although randomisation should ensure that confounders are balanced between groups). We will present the results with 95% confidence intervals. The primary analysis will be an intention to treat analysis based on finding the differences proposed. We will specify *a priori* key subgroups as potential effect modifiers based on an updated literature review prior to analysis (currently we specify baseline symptom severity, and GPs' view of whether the infection is viral or bacterial). We will also perform secondary analyses: a) a per protocol analysis, and also b) an equivalence analysis if appropriate (having established in our qualitative work what patients regard as equivalent). The clinical and demographic characteristics of a) eligible patients not consenting, and also b) those not followed up, will be compared to assess respectively possible selection and non response bias.

Our key presentation of the data will be of the main symptomatic outcomes alongside the data on antibiotic use and side effects from antibiotics

Economic analysis.

The proposed economic analysis is informed by the likely directions of changes in both costs and benefits are summarised in Table 1. This shows that cost effectiveness may not be an issue. Only short term cost differences will be captured in the trial. Long term cost effects of reduced antibiotic resistance can only be estimated from the literature, and are likely to be highly uncertain.

Table 1

Likely changes in costs and health effects due to RADTs (or rule)

RADTs (or rule) Antibiotic use	Cost effects Short term Up (cost of tests, + medicalisation) down	Long term Up (medicalisation) Down (less costs due to AB resistance)	Health effects Short term Unchanged or improved Up (fewer side effects)	Long term Unchanged or improved Up (Less AB resistance)
Net effects	?	?	Up	Up

The table indicated that net cost effects are uncertain but benefits likely to increase, modestly in short term, perhaps more in longer run, but subject to uncertainty. If costs were reduced, then RADTs would be dominant (benefits up, costs down). Only if costs increase is cost effectiveness an issue.

Short term costs depend on whether RADTs or a rule is preferred, as the costs of the latter would be low. If RADTs were preferred, their increased could lead to reduced cost per test over time (whether short or longer term). Reduced antibiotic use would reduce costs immediately. Medicalisation in the short term would increase costs. Thus net short term net costs could move up or down.

Longer term costs depend on the balance between the increased costs of medicalisation (long term) and the possibly reduced costs due to reduced AB resistance. As neither of these are likely to be established with any certainty in the trial (follow up 1 year) various assumptions will have to be made and tested in sensitivity analysis. As costs in the future would be reduced to net present values by discounting, their timing would also be important. Overall, it seems possible that a rough balance of costs may prevail on long term costs.

The economic analysis will provide:

i) a cost consequences analysis plus a simple cost effectiveness model to be used for sensitivity analysis linking costs to each of the main outcomes in the trial, and

ii) a systematic review of the literature on costs effectiveness of reduced antibiotic prescribing which would be included in the model as appropriate. Further work might then be deemed worthwhile or not, an issue which would be discussed with NCCHTA and a case made for further resources if appropriate.

The cost of intervention and follow-up related service use, including the time taken to train staff, surgery attendance, admissions and referrals, will be collected in the trial. The major increment in health service costs associated with advice to use antibiotics and/or RADTs are likely to be due to the time taken in the index consultation, and the effect on subsequent consultation behaviour. ^{19 39} Resource use data will be collected by notes review, GP and nurse documentation (e.g. of consultation time) and patient self-report. Although our primary analysis will be from the health service perspective we are also interested in the personal costs of managing sore throat. Thus during piloting and in qualitative work we will explore the range of resource use - e.g. pharmacy use, transport to pharmacy and to surgery, time taken off work/school etc – to make sure we are not missing important costs. During this phase we will also explore streamlined computerised methods of collecting NHS data on resource use from GP notes since most practices are likely to be computerised. We will model the potential long-term economic costs and health benefits by extrapolating the trial's results based on assumptions about behaviour change among GPs and patients. The potential impact of any new generation rapid test will be included in post trial modelling.

Unit costs will be based on national rather than local unit costs wherever possible to aid generaliseability of the results. Where unit costs are lacking they will be based on gross staff costs. The first phase of analysis will be to perform a cost-consequence analysis where the health service costs and consequences of the different strategies are compared – symptom duration, symptom severity, quality of life in the immediate episode, antibiotic use, side effects of antibiotics (diarrhoea, rash). A simple model will be constructed to estimate incremental cost per moderately bad sore throat prevented, per day with sore throat, with and without side effects. The implications of reduced antibiotic use and changed antibiotic resistance will be derived from a systematic review of relevant studies. While this element is difficult to quantify, ignoring it would be to set these key effects to zero. These longer terms changes in costs and benefits will be included in the model. Sensitivity analysis will explore plausible scenarios and the scope for further more detailed work

Assessment of the potential effect on clinical behaviour.

This sub-study will allow us to understand some of the key issues in applying the trial evidence in practice. A Judgement Analysis (JA) study based on social judgement theory ⁴¹ will be used at the end of phase II to estimate the impact on GP behaviour of the trial results (availability of RADT information and/or clinical scores) in their assessment of patients. We will present the study results to both participating GPs and a further sample of 'naïve' GPs. We will construct a series of vignettes ⁴²presenting combinations of clinical characteristics (cue profiles), including RADT results and/or clinical scores.

The Social Judgment Theory advocates a 'representative design' ⁴³, therefore vignettes should be representative of patients that doctors deal with in their practice. To this effect, cue profiles will be constructed from the patients participating in phase 1. Out of these, a certain number of cue profiles will be randomly selected. The number will depend on the number of cues that we decide to include – as a rule-of-thumb, 5-6 cues require a minimum of 30 cue profiles, but feasibility (stamina and patience of GPs) argues for a limited number of cues and cue profiles. Vignettes will be presented to GPs who will be asked to estimate the likelihood of each patient having streptococcus (on a 0-100 VAS), and to decide whether they would prescribe antibiotics or not. The judgment and treatment policies of each GP will then be modelled as separate regression equations. These equations will show which cues each GP actually used in assessing likelihood of infection and making treatment decisions (a cue is considered used if its regression co-efficient is significant). We hypothesise that GPs who took part in the main trial are more likely to use the RADT results or the clinical scores than 'naïve' GPs both to assess likelihood of streptococcus infection and to decide about treatment⁴⁴. To assess consistency of cue use and judgments/decisions, the same vignettes will be presented to the GPs a week later in a different order. Development and preparation of the vignettes will commence during the last 9 months of the study, but the final version of the vignettes can only be sent to the GPs once we have the results of the trial. We will therefore analyse the JA study in the penultimate month of the proposed study period allowing a month for write up.

Risk and benefits for trial participants

Since the study will use existing widely practiced strategies (but used in an ad hoc manner) there should be no risk to participants. All participants will be advised to return to the doctor if their symptoms are worsening. Major complications are unlikely in this sample¹⁹, and given structured advice to patients – probably better information than is normally available in routine care - the standard of care they receive is likely to be higher than routine practice. We have chosen the control group to be delayed prescription which provides both a way of minimising antibiotic use, minimising the medicalisation of illness, reducing return rates to the surgery, and a safety net for patients: it is not associated with any higher risk of complications.^{29;31}

Independent supervision

We will nominate a Chairman and two independent members, one of whom will be a statistician, to form a trial steering committee (TSC) which will meet early in the feasibility phase, and thereafter annually unless there are problems in which case more frequent meetings will be arranged.

Recruitment.

The current research climate in primary care makes robust recruitment essential. To ensure recruitment we will book nurse sessions in advance with adequate reimbursement (for both opportunistic referrals, and the invited community sample), and very conservatively assume that 1:3-4 sessions will be receive a referral, of these 1:3-4 parents agree, and that up to two full winters may be needed for phase I, and two for phase II. Three centres are needed (Southampton;Birmingham and Oxford), and Oxford's experience of recruiting children for such studies will be invaluable. In recent years in the difficult research climate in primary care our three centres have shown that they can recruit both adults and children in the numbers required for the successful completion of this study. We are keenly aware of the issue of feasibility, and agree that for consultations for some GPs on some days there may not be time - which is why we have assumed conservatively that recruitment may be as little as 1/2 of what we expect in one winter, and have gone further to allow two winters for both phases. We will explore the issue of any possible bias due to differential recruitment rate among GPs in analysis, but previous studies have suggested little evidence of recruitment bias.^{27;30}

The clinical proformas, and taking of the two double throat swabs, provides the main work for GPs/nurses. The clinical proformas are very simple, and they have already been piloted, and so has the taking of throat swabs. One of the arguments for the feasibility study is to be able to confirm recruitment rates, potentially overcome any issues of feasibility, and as necessary widen the net of GPs (and in the worst case scenario of course stop the study, and thus minimise risk to the NCCHTA).

The GPs we are recruiting will all be part of local Networks. Our group has a wide experience of recruitment and retention of GPs and patients to primary care trials. A number of strategies can be utilised to maintain GP recruitment including recruitment holidays, electronic reminders, Network newsletters, and incentives - so GPs will not be allowed to 'forget' the study. (Also see trial management).

Will recruitment and logistic organisation for PRISM overlap with the MRC DESCARTE study? The proposed study for this application (PRISM) is more intensive than the DESCARTE study – with clinical sampling. Therefore PRISM requires more support than the very simple DESCARTE study. Our approach will be to target research practices for PRISM, with local nurses and the RA in each centre providing support to groups of practices, i.e. we will be targeting particular practices to perform PRISM. In reality it will not be 'either' PRISM 'or' DESCARTE: there will be no competition between the studies since we are using the same baseline clinical proforma for both studies. Thus although the operation and data management of the studies will be completely independent, the PRISM data can contribute data to the data set for DESCARTE and the PRISM patient information leaflet will consent patients to the documentation of adverse events (i.e. the main outcome in DESCARTE; we would have consented patients to this anyway even if DESCARTE had not been funded).

Trial management

The Trial management group will meet 2 monthly initially, then 6 monthly if progress is good, or more often as needed. The study team will pay close attention to both recruitment retention and performance of GPs/practices. Some GPs will certainly stop recruiting; as with all our studies we will maintain recruitment of GPs throughout the study period.^{27;30;39}

Underperformance will be dealt with initially by letters from each regional coordinator to GPs, then visits to GPs (from the local champions in each Network, the overall study coordinator, and applicants and PI as necessary). How the problem is dealt with will depend on the particular issues rasied e.g. clarity of the proforma or how to document clinical features (which can be clarified), how most efficiently to recruit (examples of good practice can be provided from the other Networks) etc. If performance in one year is poor and remains poor and cannot be improved in the last resort we will transfer the funds to the better performing practices in addition to continuing to recruit practices.

The new UKPCRN arrangements will also hopefully help in managing Network performance.

Project timetable.

Oct 2006-March 2007 Recruit practices, and feasibility phase (pilot, train nurses; obtain ethics and RM+G approval for all sites; perform qualitative work to explore patients perceptions);

Feb 2007- Dec 2007 recruit patients for Phase I (1 winter);

Jun 2007 – August 2007 prepare for phase II (including completing the economic modelling exercise and pilot recruitment);

August 2007-December 2007 Phase II pilot recruitment; Jan 2008-April 2010 recruit patients

Jan 2010-June2010 follow-up, notes searching and data cleaning, development of vignette study and agreement from GPs to participate

June – September 2010 finalise data collection/analysis report writing, vignettes Consumers

There is no national consumer group associated with the management of sore throat, but we will invite 2 lay members from one of our practices to join the trial management group (as we have done in a similar validation study funded by the NCCHTA of urinary dipsticks). The perspective of consumers will also be explored during the qualitative phase, and their perceptions incorporated into the trial materials and procedures.

Justification of Support. We need:

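### The 242 per group gives 90% power for a three-group global test, but each of the two RADT comparisons behind the 1% level has about 85%

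*Protocol*

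**What the plan says.** Protocol, Sample size Phase II, primary outcome paragraph. The levels are set in the opening words, "Primary outcome: symptom severity (alpha= 0.01:beta=0.1". The effect is 0.33 SD between RADT and the control groups, "assuming both control groups are 0.33 SD higher than the RADT group". The size "requires a minimum of 134 per group (for alpha=0.05,beta=0.2) but preferably for (for alpha=0.01 and beta=0.1), 242 per group", which becomes "909 patients in total allowing for 20% loss to follow-up of diary information". The stricter alpha is explained as an allowance for type I error "with 2 comparisons between RADT and the other two groups", and also for more than one outcome (severity and duration). The stricter beta is there so that an effect on the primary outcome is not missed.

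Footnote 1 to the Phase II sample size table. "We used the NQUERY multiple group sample size programme for three groups", with the clinical score and control groups assumed alike. The footnote adds that fewer patients per group will be needed if control does worse than clinical score, and that the cells count patients with complete data.

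Statistics analysis section. Diary scores are analysed by analysis of covariance, with control for confounders if appropriate. On reporting: "We will present the results with 95% confidence intervals". The 1% level is not mentioned again.

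**The concern.** Phase II compares management by RADT with a clinical score and with delayed prescribing. Those are two pairwise questions, and the protocol gives them as a reason for choosing 1%. A global three-group test answers a different question: whether the three means differ anywhere. A significant result does not show that RADT differs from either comparator. If the sample size belongs to the global test, the 10% miss rate that the protocol wanted for its primary outcome does not apply to the comparisons that will be reported.

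The footnote shows how this can mislead. A wider spread of the three means helps the global test, but the power of RADT against clinical score does not depend on how the third arm fares.

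The level matters too. If the primary contrasts were read from 95% intervals, the multiplicity allowance that drove the sample size would not operate.

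**Working it through.** **Inputs.** From the protocol: effect 0.33 SD with means 0, 0.33, 0.33; alpha 0.01 and beta 0.1; 242 completers per group; 20% diary loss. Assumptions: equal allocation (the block sizes are multiples of 3), two-sided pairwise tests (sidedness is not stated) and no covariate gain.

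**1. Reproduce the plan's figure.** Global F test, 2 and 3(n − 1) df, noncentrality n × (2/3) × d².
- n = 242: 242 × (2/3) × 0.33² = 17.57; critical F at 1% with 2 and 723 df = 4.63; power 90.06%. At n = 241 it is 89.9%.
- The same method gives 193 (1%, 80%) and 134 (5%, 80%), and all nine continuous cells of the table. A 2-df chi-square gives all 15 proportion cells.
- Loss: 242/0.8 = 302.5, rounded up to 303; 303 × 3 = 909.
- A two-sided pairwise formula gives 274, 215 and 145 where the table has 242, 193 and 134. A one-sided 1% pairwise test gives 240, close to 242, but does not explain the other cells.

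The table is therefore a global-test table, as its footnote indicates.

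**2. Power of each RADT contrast at 242.** Two-sample t test, noncentrality d√(n/2) = 0.33 × √121 = 3.63.
- Two-sided 1%, critical value 2.586: power 85.1% (85.4% by the normal formula).
- Both contrasts significant at 1% (correlation 0.5 through the shared RADT arm): about 76%. At least one: about 94%.
- n for 90% per contrast: 2 × (2.576 + 1.282)²/0.33² = 273.3, so 274 by the normal formula and 275 by t. With 20% loss, 3 × 275/0.8 = 1031.3, so 1,032 patients against 909.

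**3. The footnote.** Illustration only, with the control mean assumed at 0.5 SD and clinical score kept at 0.33 SD. The global test at 1% then reaches 90% with 137 per group. At 137, RADT against clinical score has noncentrality 0.33 × √68.5 = 2.73 and power of about 56%.

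**4. What the level changes, at 242 per group.**

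| Level per contrast | Power per contrast | Family-wise error, two contrasts on severity |
|---|---|---|
| 1% | 85% | 1.9% |
| 5% | 95% | 9.0% |

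**5. Covariate gain.** With covariates explaining a share R² of outcome variance, the required n shrinks by (1 − R²). To bring 275 down to 242, R² = 1 − 242/275 = 0.12. The protocol gives no value, so a range is shown for power per contrast at 1%: R² = 0, 85.1%; 0.05, 87.2%; 0.10, 89.2%; 0.12, 90.0%; 0.20, 92.9%.

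**6. Secondary outcomes at the 909 target**, pairwise at 5%. Reattendance (38% v 27%): 909 × 0.9/3 = 272.7, so about 272 per group, power about 78%. Beliefs (57% v 72%) at 242 per group: about 93%.

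**The case against.** The strongest reply is that nothing was miscalculated. The 90% is right for the test that was sized, the footnote discloses that test, and the protocol nowhere states 90% for each contrast separately. That stands, and the point is a mismatch rather than an arithmetic error. It does not remove the point, because the protocol ties its alpha to the two RADT comparisons and its beta to not missing an effect on the primary outcome.

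A second reply is that the shortfall is modest. With each of two contrasts at 2.5%, power at 242 would be about 92%; RADT against the two comparators pooled would have about 95% at 1%; and analysis of covariance may recover the gap. All true. But the protocol chose 1% to cover multiple outcomes as well, it describes two comparisons rather than a pooled one, and it takes no credit for a covariate.

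A reader might infer several stronger things that the document does not support:
- That the 1% level has been given up. Presenting 95% intervals is compatible with testing at 1%, and the decision rule may sit in an analysis plan that is not shown.
- That the trial has both low power and inflated error. These are alternatives: 85% power goes with 1%, and 9% family-wise error with 5%.
- That the sentence on reattendance, "This is the limiting sample size calculation although not the primary outcome", contradicts the primary calculation. In completers it does not: 254 per group against 242. Only the different loss rates put 909 above 849.
- That the secondary outcomes have the contrast power found at 254 and 152 per group. At 909 recruited, the groups are larger.

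**Conclusion.** The point holds as a mismatch between the test that was sized and the comparisons that the alpha is meant to protect. At 242 completers per group and two-sided 1%, each RADT contrast has about 85% power, so a true 0.33 SD difference is missed about 15% of the time rather than 10%; both contrasts succeed together about 76% of the time. The footnote's remark about needing fewer patients is valid for the global test only. The failure to restate 1% in the analysis section is a gap in carry-through, not evidence of a 5% decision rule.

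These figures rest on two-sided tests, equal allocation, the protocol's own pattern of means and no covariate adjustment. The shortfall would disappear if baseline covariates explained about 12% or more of outcome variance, which the protocol does not show.

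**What to change.** 1. State that 242 per group gives 90% power for the global test, about 85% for each RADT contrast and about 76% for both at 1%. Limit the footnote's remark about fewer patients to the global test.
2. Name RADT against clinical score and RADT against delayed prescribing as the primary inference, judged at the 1% level already chosen. Give 99% intervals for these two and keep 95% elsewhere.
3. Pre-specify baseline symptom severity and prior duration of illness as covariates of the primary analysis of covariance, in place of adjustment if appropriate. Severity is on the baseline clinical sheet, and duration has to be known to apply the two-week entry limit. State that a joint R² of about 0.12 is the assumption under which 90% per contrast is recovered; a lower value leaves power between 85% and 90%.
4. If secondary power is restated, give it at the 909 target: reattendance about 78% per contrast, beliefs above 90%.

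The cost is protocol and analysis plan wording, a less favourable stated power, and intervals about 31% wider for the two primary contrasts (2.576/1.960 = 1.31). No extra patients are proposed.
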